Official Title of the study: Project Impact: An Innovative Approach to Weight Loss Maintenance NCT number: NCT02363010 Date of the document: August 1, 2020

Design and Randomization

This study was a three-arm, randomized controlled trial. The study was approved and monitored by the Drexel University institutional review board and preregistered at clinicaltrials.gov (Clinical Trials Identifier: NCT02363010). Participants provided informed consent during enrollment, which was conducted by the research coordinator and research assistants. The statistician conducted randomization using a random numbers table. Participants, counselors, and other study staff were blind to allocation, with no access to allocation data during Phase I. During Phase II, three different forms of behavioral treatment were tested and only outcomes assessors remained blinded to condition. An independent officer completed data and safety monitoring.

Participants

Participants were recruited from the community for this study from 2014 to 2016. Inclusion criteria were: BMI 27 – 45 kg/m² (measured in clinic), age 18-70 years, and completion of all steps in the enrollment process. Exclusion criteria were: medical or psychiatric conditions that could pose a risk during lifestyle modification or significantly limit the ability to begin a program of PA; history of bariatric surgery; current use of weight-affecting medication; weight loss of 5% or more in the past 6 months; current pregnancy, lactation, or plans to become pregnant during the study period; participation in or plan to participate in another weight loss program during the study period; having an immediate family member or household member participating in the study. Participants received compensation for assessment visits as follows: \$25 for baseline, \$25 for month 6, \$25 for month 12, and \$50 for month 18.

During project planning, estimates of the necessary sample size varied from 300 to 350, depending on attrition. At project launch, a final sample of 320 participants was selected, with

the assumption of up to 30% attrition, to provide 81% power to detect a medium effect size of weight loss or MVPA. Power analyses accounted for a three-level hierarchical structure, with repeated measures for each participant in a group within one of the three intervention arms, assuming a within-subject correlation of 0.5 and a within-group correlation of 0.05 (estimated from pilot data). A medium effect size was chosen because 1) an effect of that size may be needed to justify a departure from standard behavioral treatment (McGough & Faraone, 2009), 2) previous research comparing ABT to BT has observed a medium effect size for a primary outcome (Forman et al., 2016), and 3) medium or larger effect sizes have been observed for the comparison of weight loss in those engaging in high versus low MVPA (Tate, Jeffery,

Sherwood, & Wing, 2007).

Shared Intervention Components

Phase I (Months 1 to 6) consisted of 16 closed-group sessions, held on a weekly (8 sessions) and then bi-weekly (8 sessions) basis, with approximately 12 participants in each group. During Phase I, all participants received BWL treatment designed to induce 10% weight loss, with materials adapted from Look AHEAD (2006) and the Diabetes Prevention Program (2002). Participants were instructed to keep daily records of dietary intake. Calorie intake was emphasized as the key determinant of weight loss. Stimulus control, problem solving, goal setting, and social support skills were taught. Participants were instructed to gradually self-monitor and increase free-living MVPA, with a goal of maintaining 250 minutes per week of MVPA by 6 months and beyond. Participants were instructed to conduct MVPA in bouts of 10 minutes or more. Participants self-reported weekly MVPA minutes and average calorie intake during each session's group check-in, and counselors also provided brief written feedback on self-monitoring records on which exercise and dietary intake were reported. Counselors had

doctoral-level psychology training. In Phase I and II, all group sessions began with private measurement of weight.

Phase II Interventions (Months 7-18)

Group sessions (14 total) continued in Phase II, beginning with 7 weekly sessions followed by 4 bi-weekly sessions. The final three sessions were held in Months 12, 15, and 18. Each participant also had a 15-minute phone call with a counselor between the quarterly sessions (three calls total) to promote continued engagement. Supplementary Table A details the intervention content in each arm.

Behavioral Therapy (BT)

The BT condition in Phase II continued to be based on Look AHEAD (2006) and Diabetes Prevention Program (2002) materials. Sessions were designed to apply traditional behavioral skills such as problem solving and goal setting to the challenges of long-term lifestyle modification. Approximately two-thirds of intervention content and session time was designed to be applied to eating behavior, with a secondary emphasis on PA.

Behavioral Therapy with Physical Activity Emphasis (BT+PA)

In the BT+PA condition, approximately two-thirds of session time and content was designed to focus on PA, with one-third of session time focused on eating behavior. The intervention was created by adapting material from the Look AHEAD (2006) and Diabetes Prevention Program (2002) protocols to be PA-focused, and by incorporating techniques from Michie's behavior change taxonomy (Michie et al., 2011). For example, when a session on "maintaining motivation" was conducted, exercises and discussion in session were focused primarily on enhancing motivation for PA. As another example, the application of goal setting skills was primarily focused on PA goals. Progress towards PA goals, particularly the barriers or facilitators of such progress, was reviewed in each session in greater detail than occurred in the BT condition. PA, rather than eating behavior, was the primary target for problem solving skills. Group leaders frequently encouraged development of implementation intentions for PA.

Acceptance-Based Behavioral Therapy with Physical Activity Emphasis (ABT+PA)

The amount of emphasis on promoting PA was designed to be similar in BT+PA and ABT+PA. However, in ABT+PA, acceptance-based behavioral skills were taught, rather than traditional behavioral skills. This approach was adapted primarily from an acceptance-based weight loss protocol (Forman & Butryn, 2016). A key goal was to increase awareness of internal experiences that shape PA behaviors. The approach validated the sense that many aspects of PA are "uncomfortable," meaning that it can be difficult to tolerate the thoughts (e.g., "I would rather be doing something else"), emotions (e.g., boredom), urges (e.g., to avoid or end exercise), or physical sensations (e.g., sweating) that occur while one attempts to engage in PA or while making PA-related decisions. Participants learned how to respond to internal experiences with a stance of non-judgmental acceptance, which enables flexibility (i.e., the ability to engage in a wide range of behaviors, regardless of the accompanying internal experiences). Ultimately, acceptance was intended to promote long-term persistence in PA. Values clarity, which is integral to the use of acceptance skills, included the ability to consider the ways in which being physically active enables pursuit of what is most important in one's life (e.g., being physical fit can make travel or community service more feasible). Participants were encouraged to use their "long-term mind" to have a heightened awareness of their values at moments of PA-related decision making, rather than being driven by transient internal experiences.

Measures

Assessments were conducted at Months 0, 6, 12, and 18.

Demographics. Race, ethnicity, sex, age, and education were self-reported at baseline.

Moderate-to-Vigorous Physical Activity. Participants were instructed to wear ActiGraph (Pensacola, FL) GT3X tri-axial, solid state accelerometers for all waking hours for 7 consecutive days at each assessment point. ActiLife software was used with cutpoints defined by Troiano et al. (2008) to identify bouts of 10 minutes or more in which PA of moderate-to-vigorous intensity was detected. Data were considered valid and included in data analyses if the participant wore the accelerometer for at least 10 hours each day for 4 or more days.

Weight and Height. Participants' weights were measured by research staff with a Tanita® model WB-3000 digital scale, with participants wearing light street clothing. Height was measured with a stadiometer. Measurements were taken two times and averaged.

Half-Mile Walk Time. After a 30 second warm up period, participants were asked to walk 0.5 miles on a treadmill in the lab. Participants were shown how to adjust the speed of the treadmill and were instructed to walk as briskly as they could, adjusting the speed as they wished throughout the task. Participants were told that the task was a measure of physical fitness. Shorter times indicated a greater level of cardiorespiratory fitness (Mayorga-Vega, Bocanegra-Parrilla, Ornelas, & Viciana, 2016).

Waist Circumference. Waist circumference was measured horizontally at the umbilicus. Measurements were taken two times and averaged if the measurements were discrepant by less than 2.0 cm (measurements were re-taken if the discrepancy was greater).

Treatment Fidelity. All treatment sessions were audio-recorded, and 10% of recordings were rated for counselor fidelity to the treatment manual. The treatment manual was organized so that each session included a check-in, two or three topics of discussion or activities designed to build a particular behavior skill, and assignment of skill builders. Each of these sections of the

session was rated on a 1-10 scale for adherence, with adherence defined as the extent to which the material was delivered as specified in the manual, including pacing of each topic. BT sessions also were given a rating for the extent to which the counselor avoiding PA contamination (i.e., limited the focus on PA to that specified in the manual) and BT and BT+PA conditions were rated for avoiding ABT contamination.

Data Analysis Plan: Results Through 18 Months

Data were analyzed in R (Team, 2013) and SPSS Version 25 (IBM Corp., 2017). Data distributions and assumptions were examined before conducting any formal statistical test. Analyses were conducted on an intent-to-treat basis with multiple imputation via the mice package in R (van Buuren, 2011), such that all participants enrolled in the trial were included in analyses (BT: n = 110, BT-PA: n = 105, ABT-PA: n = 105), with two exceptions noted for exploratory analyses. We performed the analyses for each of the imputed datasets separately, and combined the test statistics across datasets based on Rubin's rule as implemented in the miceadds package in R (Robitzsch, 2017). To account for the zero-inflated distribution of MVPA, compound Poisson linear regression models (cplm; Zhang, 2013) were used to test the treatment effect on MVPA at 12 and 18 months separately, controlling for MVPA measured at earlier time points. The effect of treatment on percent weight loss at 12 and 18 months were examined separately using general linear models controlling for weight measured at earlier time points. General linear models also were used to examine the treatment effect on half-mile walk time and waist circumference. Moderation analyses were used to examine whether the effect of treatment condition on MVPA or percent weight loss depended on sex, baseline BMI, baseline MVPA, weight loss in Phase I or change in MVPA during Phase I. Additional exploratory analyses using general linear models were performed to further understand the relationship between specific

levels of MVPA (regardless of condition) and weight loss outcomes among participants (n = 271) who provided data at 6 months; this subsample was chosen to reduce missing data to allow for greater precision in estimating dose-response for this analysis.

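### The imputation step does not name the weights taken at every group session; if they are left out and dropout follows regain, maintained loss is overstated

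*Combined protocol and SAP*

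**What the plan says.** All places are in the combined protocol and SAP.

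- **Session weights.** Shared Intervention Components: "In Phase I and II, all group sessions began with private measurement of weight". Phase I has 16 sessions. For Phase II, the section Phase II Interventions (Months 7-18) says: "Group sessions (14 total) continued in Phase II, beginning with 7 weekly sessions followed by 4 bi-weekly sessions" and "The final three sessions were held in Months 12, 15, and 18".
- **Outcome weights.** Measures: "Assessments were conducted at Months 0, 6, 12, and 18". Under Weight and Height, participants' "weights were measured by research staff with a Tanita" scale. Session weights are not listed among the measures, and the scale and measurer used at sessions are not described.
- **Analysis.** Data Analysis Plan: Results Through 18 Months: "The effect of treatment on percent weight loss at 12 and 18 months were examined separately". The plan describes the models for this outcome as "general linear models controlling for weight measured at earlier time points". Which earlier time points are meant is not stated.
- **Missing data.** Same section: "Analyses were conducted on an intent-to-treat basis with multiple imputation via the mice package in R", with all 320 participants included. The section names no imputation predictors, states no missing-data assumption and describes no sensitivity analysis.

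**The concern.** This is a maintenance trial. Phase I is designed to bring about a 10% loss, and what happens afterwards is the question. Most Phase II sessions fall between the Month 6 and Month 12 assessments. A participant who attends for some weeks after Month 6, regains, and leaves before Month 12 has the regain on record at sessions, but the last assessed weight is from Month 6, before that regain. An imputation that sees only assessed weights gives this person the course of those who stayed with a similar Month 6 weight.

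If people leave because they are regaining, missing weights are not missing at random given the assessed weights alone. They come much closer to it once session weights are conditioned on. At stake are the arm means for maintained loss at Months 12 and 18, to a lesser extent the comparison between arms, and the precision of the imputed values.

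**Working it through.** **1. The plan's own counts.** The plan gives no figure for the effect of missing weights, so the check starts from its schedule and sample.

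- Phase II sessions: 7 + 4 + 3 = 14, which agrees with the stated total.
- If sessions start straight after Month 6 (assumed), the first 11 take 7 + 4 × 2 = 15 weeks. Then 15 × 12/52 = 3.5 months, so they run to about Month 9.5.
- Between the Month 12 and Month 18 assessments there is one session, at Month 15.
- The analysis plan gives 271 participants with 6-month data: 320 − 271 = 49, or 15.3%, without. It does not say which data these are or whether any of the 49 returned.
- The sample-size text allows for up to 30% attrition.

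**2. Size of the effect on one arm mean.** Overstatement = p × u, where p is the proportion missing at Month 18 and u is the mean regain among leavers that the imputed values miss.

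The documents give no regain rates or dropout mechanism, so all of the following is assumed: mean loss 10% at Month 6 (SD 6), mean regain 0.3 points per month (between-person SD 0.3 or 0.5), measurement noise SD 1, a further within-person fluctuation parameter of 0.5, and a log-hazard of dropout that rises with regain since Month 6. The session calendar is that of step 1. Sequential regression imputation from assessed weights only, including Month 12 where observed, with 30% lost by Month 18, overstates mean loss as follows (percentage points):

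| Log-hazard per point of regain | Regain SD | Month 12 | Month 18 |
|---|---|---|---|
| 0 | 0.3 or 0.5 | 0.00 | 0.00 |
| 0.1 | 0.3 | 0.05 | 0.11 |
| 0.1 | 0.5 | 0.08 | 0.18 |
| 0.2 | 0.3 | 0.08 | 0.19 |
| 0.2 | 0.5 | 0.15 | 0.35 |
| 0.4 | 0.3 | 0.13 | 0.38 |
| 0.4 | 0.5 | 0.21 | 0.61 |

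The implied u at Month 18 runs from 0.11/0.30 = 0.4 to 0.61/0.30 = 2.0 points per leaver. With 15% lost (log-hazard 0.2, SD 0.5) the figures are 0.06 and 0.16. With session weights added as predictors, every row is about zero.

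**3. Size of the effect on an arm difference.** Assumed: Month 6 loss 9% (SD 6), linear regain of 0.50 against 0.25 points per month (SD 0.45), and all dropout before Month 12, rising with regain from Month 6 to Month 9. The true Month 18 difference is 12 × (0.50 − 0.25) = 3.0 points.

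| Dropout, worse / better arm | Overstatement, worse arm | Shrinkage of difference |
|---|---|---|
| 16% / 14% | 0.26 | about 1% (0.01 × 3.0 = 0.03) |
| 22% / 18% | 0.67 | about 4% (0.12) |
| 29% / 23% | 1.18 | about 9% (0.27) |

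The overstatement in the better arm is the worse-arm figure less the shrinkage: about 0.23, 0.55 and 0.91. Most of the bias therefore cancels in the contrast. Adding one Month 9 session weight left under 0.01 points of bias, also when that weight carried extra noise of SD 1.

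**4. Precision.** Adding session weight raised R-squared for Month 18 loss from 0.47 to 0.71 under one set of assumed residual SDs, and from 0.57 to 0.75 under another. Residual variance of the imputed values falls by 1 − 0.29/0.53 = 45% and 1 − 0.25/0.43 = 42%. This gain does not depend on why people leave.

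**The case against.** A reader might infer that the session weights were not used. The documents do not support that. The analysis plan lists no imputation predictors at all, so it neither includes nor excludes them, and its wording on earlier weights is open too. What stands is that the plan does not name them.

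A reader might also infer that maintenance is overstated in every arm and that the arm difference is diluted. Neither follows. Overstatement needs dropout to depend on regain that the assessed weights do not carry, and no section describes why people left. Dilution further needs regain or dropout to differ by arm.

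The illustration in step 3 is favourable to the concern in four ways, and each of these points stands:

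- It places all dropout before Month 12. Someone who leaves later has an assessed Month 12 weight. Making that weight available cut one worse-arm bias from 0.63 to 0.15 points, about 75%. With half the leavers having it, a range of 0.3 to 1.3 points became 0.2 to 0.8.
- Every leaver is given a session weight. Those who skip sessions before leaving have none.
- The near-zero bias after adding session weights is built in, because dropout was generated from the weights then used to impute.
- If most of the 49 participants without 6-month data had left for good (not stated), about half of the 30% allowance is used before Phase II. With worse-arm dropout held at 15%, the figures were 0.2 to 0.6 points and 2 to 5% shrinkage. Phase II session weights cannot help those 49, although late Phase I session weights might.

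Finally, it might be inferred that unblinded staff took the session weights. The plan says only that outcome assessors alone stayed blinded in Phase II; it does not say who weighed participants at sessions.

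**Conclusion.** The point holds in a conditional form. The trial collects weights at every session, describes outcome weights at four visits only, and does not name session weights in the imputation. If the imputation rests on assessed weights alone and dropout depends on regain between assessments, maintained loss is overstated by roughly 0.1 to 1 percentage point in an arm mean at Month 18, and by less at Month 12. An arm difference shrinks by about 0 to 10%. If dropout is unrelated to regain there is no bias, and only precision is lost.

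These sizes rest on assumed regain rates, SDs and dropout slopes, not on trial figures. Nothing here shows that a conclusion of the trial would change. The case for acting is that the data already exist, the change is cheap, and it improves the imputed values whether or not the bias is present.

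**What to change.** In the Data Analysis Plan, list the predictors in the mice step and include the available session weights, as percent change from Month 0, as auxiliary predictors of missing Month 6, Month 12 and Month 18 weights. A short set is enough: a late Phase I session, the last weekly and the last bi-weekly Phase II sessions, and the Month 15 session. If they were already included, saying so settles the point. Keep the assessed outcome and the analysis models unchanged.

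The cost is some data handling and a few more imputation variables, themselves incomplete because session weights exist only for attended sessions. As their scale and measurer are not described, they should only predict missing values and never replace an assessed one. They also cannot correct for regain that happens after the last attended session and drives dropout.

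### Does pooling the imputed results by their test statistics, with no number of imputations stated, cost power or make the verdict depend on the seed?

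*Combined protocol and SAP*

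**What the plan says.** The section Data Analysis Plan: Results Through 18 Months keeps all randomised participants ("BT: n = 110, BT-PA: n = 105, ABT-PA: n = 105") by means of "multiple imputation via the mice package in R". It continues "We performed the analyses for each of the imputed datasets separately" and then says the authors "combined the test statistics across datasets based on Rubin's rule as implemented in the miceadds package in R". That is everything on pooling. The number of imputations, the imputation model, the seed and the pooling function are not given, and no pooled arm difference or interval is named.

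Three other places bear on how much is imputed. The sample-size paragraph under Participants says "a final sample of 320 participants was selected", with "the assumption of up to 30% attrition". Measures says "Assessments were conducted at Months 0, 6, 12, and 18". The last exploratory analysis uses the 271 people "who provided data at 6 months; this subsample was chosen to reduce missing data".

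**The concern.** Rubin's rules normally average the arm estimates and add the between-imputation variance to the within-imputation variance. A sentence about combining test statistics points to a different device, often called D2. It works only from the test statistic of each imputed dataset and judges the missing-information penalty from their scatter. With few imputations that scatter is poorly estimated, so the test loses power and its p-value moves with the random seed.

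Missing data are not trivial here, and the imputed analyses are the main ones. If the literal reading and a small number of imputations both applied, a real difference between arms would be missed more often, and a second analyst with the same data could reach the opposite verdict. A combined statistic alone would also not tell readers whether the medium effect used to justify the sample size had been reached.

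**Working it through.** **Inputs from the documents.** N = 320; arms 110/105/105; attrition up to 30%; within-subject correlation 0.5; within-group correlation 0.05; about 12 per group; 271 with month-6 data. Missing at month 6: (320 − 271)/320 = 49/320 = 15.3%.

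**Assumptions.** The number of imputations m is varied because it is not stated. Alpha is 0.05 two-sided. Dropout is random and monotone.

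**The plan's own power.** One route reproduces the 81%:
- completers per arm: 320 × 0.7/3 = 74.7
- variance factor: (1 − 0.5²) × (1 + 11 × 0.05) = 0.75 × 1.55 = 1.1625, so SD = 1.078
- standard error for d = 0.5 (medium, assumed): 1.078 × √(2/74.7) = 0.176
- 0.5/0.176 − 1.96 ≈ 0.87, giving power of 80.9%.

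**The two rules.**
- Pooling estimates: total variance T = Ū + (1 + 1/m)B, where Ū is the mean within-imputation variance and B the between-imputation variance. The Wald test on the pooled arm coefficients is D1.
- Combining statistics: D2 = [W̄/k − ((m+1)/(m−1))r]/(1 + r), with r = (1 + 1/m) × var(√W). W is the Wald statistic in each imputed dataset, and k = 2 for three arms. The penalty r rests on m numbers only.

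**Simulation.** Month-18 normal outcome, adjusted for months 0 and 6; top arm at 0.4 SD (assumed); 30% missing; 2,500 trials per scenario. Power in %:

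| m | middle arm 0 SD: statistics | estimates | gap | middle arm 0.2 SD: statistics | estimates | gap |
|---|---|---|---|---|---|---|
| 5 | 74.4 | 80.3 | 5.9 | 61.6 | 68.4 | 6.8 |
| 10 | 83.7 | 85.3 | 1.6 | 71.5 | 73.7 | 2.2 |
| 20 | 86.0 | 86.4 | 0.4 | 74.0 | 75.0 | 1.0 |
| 30 | 86.6 | 86.7 | 0.1 | 74.9 | 75.1 | 0.2 |

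At m = 50 there is no difference.

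**Variations at m = 5.**
- 15.3% missing: 90.0 vs 91.9% and 80.0 vs 81.6%, gaps of 1.9 and 1.6. Repeat simulations put this at about 2 to 3 points.
- Month 12 added as a covariate, 30% missing: 48.5 vs 53.1% and 39.1 vs 42.8%, gaps of 4.6 and 3.7.
- Top arm at 0.5 SD, middle arm at 0: 90.6 vs 94.7% at 30% missing; 98.5 vs 99.0% at 15.3%.
- Compound Poisson MVPA (30% zeros assumed), 30% missing: 45.1 vs 50.6%, and 35.9 vs 36.7%, the second within simulation error. At m = 30: 56.7 vs 56.8% and 40.9 vs 41.3%.

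**Effect calibrated to about 81% power, missing information about 0.30.** Statistics vs estimates: m = 5, 68.3 vs 74.3%; m = 20, 79.5 vs 80.5%; m = 50, 80.9 vs 81.1%; m = 100, 81.2% for both. For a single two-arm contrast at m = 5 the gap is only 75.3 − 73.5 = 1.8 points.

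**Seed dependence, 30% missing.** Verdict flips on re-imputation: 20.5 to 23.7% (statistics) vs 12.1 to 15.2% (estimates) at m = 5; 4.3 to 6.7% vs 2.3 to 4.7% at m = 30.

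**Type I error, normal outcome.** 4.5 to 6.0% (statistics) vs 4.9 to 6.0% (estimates). It was not checked for the MVPA model. Clustering by group was not simulated.

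**The case for a change.** The strongest case for a change is that the omission is real and cheap to repair. Nothing is blacked out: the sentence is complete and leaves the number of imputations out. That number matters under either reading. With estimates pooled properly, going from m = 5 to m = 30 gains 86.7 − 80.3 = 6.4 points or 75.1 − 68.4 = 6.7 points; under the literal rule it gains 12.2 or 13.3. A reader therefore cannot tell how stable a borderline p-value is. Judging whether a medium effect was reached also needs an arm difference with an interval, whatever m was.

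The arithmetic stands, and so does the remark that the number should be on record. Two parts do not carry through to the plan. First, the loss depends on an m that nobody has shown to be small; the larger effect comes from that unknown number, not from the pooling rule the sentence describes. Second, the absence of arm differences is inferred from silence. The general linear and compound Poisson models produce arm coefficients in every imputed dataset, and combining statistics for a test does not prevent those coefficients from being pooled and reported.

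**Conclusion.** No change to the plan follows. The section is a short account, in the past tense, of an imputation analysis. Its reference to Rubin's rule fits ordinary pooling of estimates as well as the literal reading. The feared harm needs three things together: the literal reading, few imputations, and missingness near the planning ceiling. In that corner the rule costs the 3-arm weight test about 4 to 7 points of power. At 15.3% missing it costs about 2 to 3 points with five imputations, and with 30 or more imputations about 1 point or less. The error is on the cautious side: a difference may be missed, but false positives are not inflated for the normally distributed outcome. An analyst who follows the section with an adequate number of imputations reaches essentially the same result by either rule.

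Naming the number of imputations and the pooling function in the trial report would be good practice, but that is a reporting detail and not an error in the design or analysis. The figures assume random dropout, correlation 0.5 and the effect sizes shown, and they ignore group clustering. Type I error under the MVPA model remains unchecked, and month-18 missingness is not given.

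### As worded, the Month-18 models for MVPA and percent weight loss adjust for the Month-12 value, which is measured after the arms diverge

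*Combined protocol and SAP*

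**What the plan says.** The section Data Analysis Plan: Results Through 18 Months fits one model per outcome and visit. For MVPA, compound Poisson models "were used to test the treatment effect on MVPA at 12 and 18 months separately, controlling for MVPA measured at earlier time points". For percent weight loss, the effects at the two visits are "examined separately using general linear models controlling for weight measured at earlier time points". Neither sentence lists the covariate months.

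The timing comes from other sections:

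- Measures: "Assessments were conducted at Months 0, 6, 12, and 18".
- Shared Intervention Components: "During Phase I, all participants received BWL treatment designed to induce 10% weight loss". Phase I covers Months 1 to 6.
- Design and Randomization: "During Phase II, three different forms of behavioral treatment were tested". Phase II covers Months 7 to 18.

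The moderators in the Data Analysis Plan are sex, baseline BMI, baseline MVPA, and "weight loss in Phase I or change in MVPA during Phase I". All of them are known by Month 6.

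**The concern.** Months 0 and 6 are safe covariates. Treatment was common to all participants until Month 7 and allocation was concealed during Phase I, so neither value can carry an arm effect. Month 12 is different because it follows about six months of differing treatment. For a model whose outcome is at Month 18, the visits before it are Months 0, 6 and 12, and no sentence excludes Month 12 or says that the aim is change after Month 12.

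If Month 12 is in the model, the arm coefficient answers a narrower question: whether the arms differ at Month 18 among participants with the same Month-12 value. An arm that gains an advantage by Month 12 and keeps it would have that advantage understated at the final assessment, and the test would be less likely to detect it. The affected outcomes are the two on which the trial was powered.

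**Working it through.** **Which visits count as earlier**

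| Model | Visits before the outcome | Any after divergence (Month 7 on)? |
|---|---|---|
| Month 12 | 0, 6 | No |
| Month 18, read literally | 0, 6, 12 | Yes, Month 12 |
| Month 18, one shared covariate set | 0, 6 | No |

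**What the coefficient estimates.** Let e12 and e18 be the arm effects at Months 12 and 18, and b12 the partial slope of the Month-18 outcome on the Month-12 value. There is no arm effect at Months 0 and 6. In a linear model:

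- adjusting for Months 0 and 6, the arm coefficient is e18;
- adjusting for Months 0, 6 and 12, it is e18 − b12 × e12.

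**Inputs from the plan.** 320 participants, three arms, up to 30% attrition, within-subject correlation 0.5, within-group correlation 0.05, about 12 per treatment group. These give n per arm = 320 × 0.70 / 3 = 74.7 and design effect = 1 + (12 − 1) × 0.05 = 1.55.

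**Assumed, because the plan gives no value.** Pairwise d = 0.5 for a medium effect, and two-sided alpha 0.05. The correlation pattern is taken as exchangeable (0.5 between all visits) or serial (0.5 between adjacent visits, decaying with distance).

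**The plan's 81%.** With variance factor 0.75 (one covariate correlated 0.5, or the mean of two repeated measures), SE² = (2/74.7) × 1.55 × 0.75 = 0.0311 and power = Φ(0.5/0.1765 − 1.96) = 80.9%. Other formulas also come within 2 points of 81%, so the sponsor's method cannot be identified. The 81% is not in dispute, and the figures below are for single-visit models that do not re-derive it.

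**One outcome measured at all four visits, effect sustained (e12 = e18 = 0.5).** SE² = (2/n) × design effect × residual variance × inflation. The inflation, from the association between arm and the Month-12 value, is 1 + e12²/(4 × residual variance of Month 12 given Months 0 and 6).

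- *Exchangeable:* b12 = 0.5/(1 + 2 × 0.5) = 0.25. Without Month 12, residual variance is 0.667 and power is 85%. With it, the coefficient is 0.5 − 0.25 × 0.5 = 0.375, residual variance 0.625, inflation 1.094, power 61%.
- *Serial:* b12 = 0.50. Without Month 12, residual variance is 0.938 and power is 72%. With it, the coefficient is 0.25, residual variance 0.750, inflation 1.083, power 28%.

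For within-subject correlations from 0.3 to 0.9, the share removed is 19% to 32% (exchangeable) or 30% to 90% (serial).

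**Percent weight loss adjusted for weights, as the plan describes.** Two million simulated participants per case, two arms, with assumed baseline weight 100 (SD 16) and percent-loss SD 6. Percent loss at Months 6, 12 and 18 follows the correlation patterns above and is independent of baseline weight. Residual variance without and with Month 12 is 0.756 and 0.675 (exchangeable) or 0.938 and 0.756 (serial). Inflation is 1.081 when the effect is sustained. Each cell shows adjustment for Months 0 and 6 → adjustment for Months 0, 6 and 12.

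| Month-12 effect | Exchangeable: coefficient; power | Serial: coefficient; power |
|---|---|---|
| Same as Month 18 | 0.50 → 0.34; 81% → 49% | 0.50 → 0.26; 72% → 29% |
| Half of Month 18 | 0.50 → 0.42; 81% → 70% | 0.50 → 0.38; 72% → 57% |
| None | 0.50 → 0.50; 81% → 85% | 0.50 → 0.50; 72% → 80% |

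In the sustained case, 32% or about 49% of the effect is removed. A baseline SD of 12 to 20 or a percent-loss SD of 6 to 10 leaves this at 32–33% and 48–49%. Adjusting for Month 12 costs power once the Month-12 effect exceeds about 16% (exchangeable) or 21% (serial) of the Month-18 effect.

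**Upper bound on power.** With 105 per arm as enrolled and no clustering, the sustained case for weight loss gives 99% → 82% and 96% → 54%. The share removed does not change.

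**MVPA.** Compound Poisson simulation with assumed variance power 1.5, log link, 75 per arm, 20% zeros and a sustained mean ratio of 1.5; 300 datasets per case. The plan does not say whether covariates enter logged or linear.

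| Covariate form | Exchangeable: log ratio | Serial: log ratio |
|---|---|---|
| Linear | 0.391 → 0.296 (24% removed) | 0.399 → 0.219 (45%) |
| log(1 + x) | 0.394 → 0.345 (12%) | 0.403 → 0.306 (24%) |

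With no Month-12 effect, the log ratio is essentially unchanged. This simulation was not independently repeated, so its figures are approximate.

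**The case against.** The strongest reply is that this is an ambiguity and not a demonstrated error. One phrase serves a pair of outcomes, and the visits that precede both are Months 0 and 6. The plural does not point to Month 12, since the Month-12 model already has two prior visits. The Phase I moderators also favour a covariate set that ends at Month 6. This is fair, and the Months 0 and 6 reading may be what was done. But the moderator sentence does not define the covariates, and fitting the visits separately makes it equally natural to count back from each model's own outcome. Two analysts following the text faithfully could estimate different quantities.

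Second, harm needs both Month 12 in the model and an arm effect already present at Month 12. The document gives no expected Month-12 effect, and with none the adjustment gains power. This stands, and it is why the sizes are conditional. A gain in precision does not, however, restore the intended comparison when there is a Month-12 effect.

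Third, the lower power figures use post-attrition numbers and a clustering penalty, whereas the plan analyses all 320 participants by multiple imputation and names no clustering term. The upper-bound figures address this. They ignore information lost to missing data, and the share of effect removed is the same.

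Finally, no section names Month 18 as the primary time point, and the Month-12 models would still report an early advantage. Both points are true, but neither tells the reader whether the arms differ at Month 18.

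**Conclusion.** The concern holds as a defect in a stated rule. Followed literally, the plan puts a post-divergence outcome into the Month-18 models for MVPA and percent weight loss, and nothing in the document prevents it. Whether Month 12 was actually included cannot be determined. If it was not, the analysis is sound and only the wording needs correcting. If it was, the Month-18 p-values do not test the arm difference at Month 18.

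For an effect sustained from Month 12, the illustrations at correlation 0.5 remove about a quarter to a half of a linear effect and 12% to 45% of the MVPA log ratio. The size depends mainly on the Month-12 effect and the correlation pattern, neither of which the plan specifies. The Month-12 models are unaffected on either reading. This should be fixed; confidence is moderate because the intended covariate set is unknown.

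**What to change.** State that the Month-12 and Month-18 models for MVPA and percent weight loss adjust only for the Month 0 and Month 6 values. If the Month-18 models that were run included Month 12, re-run them without it. Report any Month-12-adjusted result separately, labelled as conditional on Month-12 status.

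The cost is one sentence, plus a re-run only if Month 12 was used. Some reduction in residual variance is given up (for percent weight loss, 0.756 instead of 0.675, or 0.938 instead of 0.756). If there is no Month-12 effect, power is lower than with the adjustment: 81% against 85%, or 72% against 80%.
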